Encouraging Blood Donation in Patients With a Blood Type in Short Supply – Part 2

Protocol and Statistical Analysis Plan

NCT05825300

July 3, 2023

Protocol

Scientific background

There has been a years-long national shortage of several blood types in the U.S., including in the Geisinger community. Previously, the study team collaborated with Miller Keystone, where Geisinger refers patients who wish to donate blood and from whom Geisinger receives blood for clinical purposes, on an outreach study to encourage blood donation in patients with needed blood types. The study demonstrated that, compared with a no-message control group, patient portal messages sent to patients with needed blood types increase patients' likelihood of attending donation appointments. However, results were ambiguous with respect to which of two message versions was most effective. One version, which stated that the patient had a needed blood type (blood-type message), caused a numerically, but not significantly, higher number of patients who attended appointments compared to the other version, which did not state that the patient had a blood type in need but rather informed the recipient of a general blood shortage (no-blood-type message).

Because Miller Keystone particularly values reaching new donors, the team ran a preregistered exploratory analysis to test whether the messages were differently effective for new donors compared to those who had previously donated at a Miller Keystone site. There was a significant interaction between previous donor status (previous donor, previous non-donor) and message type, such that previous non-donors were relatively more responsive to the blood-type message, while previous donors were more responsive to the no-blood-type message. However, the groups were uneven with respect to the number of patients that had previously donated. Moreover, when the analysis was limited to patients who opened their messages, this interaction effect disappeared: blood-type messages were still most effective in previous non-donors, and there was no difference in message effectiveness among previous donors. These follow-up analyses, and the unevenness of previous donors across groups, call into question the robustness of the interaction effect.

Objectives

The present study again tested whether the blood-type message is more effective than the no-blood-type message for patients with needed blood types overall, and separately for previous donors and non-donors. Messages in the present study were sent via email rather than via patient portal. Randomization occurred at the email-address level to one of the two message types to ensure everyone using the same email address received the same message (although each patient was sent an individualized message with their name; there was no no-contact control condition this time). Email addresses were excluded if they were shared by patients with different blood types. Randomization was stratified by whether all patients using the same email address are previous donors or not (email addresses shared by previous donors and non-donors were excluded).

Design

This study is a randomized controlled trial with 2 study arms.

Methods

Email addresses of patients enrolled in the study were randomized to the following arms:

1. No-blood-type message – a message that did not mention the patient had a needed blood type
2. Blood-type message – a message that mentioned the patient had a needed blood type

Randomization was stratified by previous donor status of all patients at an email address.

Power analysis

Our sample includes 40,486 patients with a total of 40,130 email addresses. 39,317 email addresses are associated with patients who are previous non-donors, and 813 email addresses are associated with patients who are previous donors.

Within the previous non-donor group, we will have 80% power to detect an increase in the primary outcome from 0.07% (the primary-outcome rate in previous non-donors who were sent a no-blood-type message in our previous study) to 0.16%, with a two-tailed alpha of .05.

Within the previous donor group, we will have 80% power to detect an increase in the primary outcome from 4.76% (the primary-outcome rate in previous donors who were sent a no-blood-type message in our previous study) to 9.87%, with a two-tailed alpha of .05.

Note that a portion of the sample will be excluded from analysis (e.g., those whose emails were not sent or bounced; see the *Analysis notes* section for details).

Project status

All emails have been sent. No outcome data have been extracted.

Statistical Analysis Plan

Primary outcome

Number of Participants Who Attended a Donation Appointment

Attended a donation appointment within 6 weeks of their message send date, regardless of whether they donated. This outcome includes patients who were unable to donate for

any reason (e.g., low hemoglobin) or patients who showed up to the appointment but decided to leave before donating.

[Time Frame: Within 6 weeks of the patient's message send date]

Question 1: Within patients who *are not* previous donors, do more patients attend donation appointments if they are sent the blood-type message compared with those sent the no-blood-type message?

Analysis 1: We will test the hypothesis that previous non-donors who are sent a blood-type message are more likely to attend a donation appointment than those sent a no-blood-type message. We will run an OLS regression with a binary predictor variable indicating whether patients were sent the blood-type message or the no-blood-type message.

Question 2: Within patients who *are* previous donors, do more patients attend donation appointments if they are sent the blood-type message compared with those sent the no-blood-type message?

Analysis 2: We will run *Analysis 1* including only patients who are previous donors.

Analysis notes

Whether or not a patient is a previous donor was determined by a data pull completed prior to randomization. Because the data on previous donors from this pull was used to stratify randomization, we will use this data pull to determine whether patients should be included in *Analysis 1* (previous non-donors) or *Analysis 2* (previous donors), even if we later learn the patient had previously donated (e.g., if they donated after the pre-randomization data pull but before the intervention began).

Analyses will be conducted on the email-address level. For each email address, if any associated patient attended a donation appointment, the email address will be “counted” as achieving the primary outcome. To ensure that our findings do not depend on patients who share an email address, we will also run the analyses above removing all patients who share an email address with another patient in the study.

All analyses will exclude patients who scheduled their appointment prior to their message send date.

Patients will be excluded from analysis if, according to our records, their emails were not sent (e.g., due to being unsubscribed from emails) or for whom our emails bounced.

Timeframes listed refer to the amount of time elapsed from the send date for a given patient. For instance, the primary outcome timeframe is 6 weeks; thus, for the purposes of this study, a

patient will be counted as having donated if they donated blood within 6 weeks of their message send date.

As a robustness check, we will rerun the analyses above on the subset of patients who open the messages, using a time frame of 6 weeks from the date each individual patient opened their message (rather than 6 weeks from the patient's message send date).

We will run an additional robustness check including only patients who scheduled an appointment within the 2 weeks following their message send date.

Recent work suggests that OLS regressions are appropriate in randomized experiments with binary outcome variables such as ours (Gomila, 2021).

Other prespecified outcomes

We will use the approaches described in *Analyses 1* and *2* above to evaluate the impact of the intervention on the other prespecified outcome measures listed in the pre-registration:

1. Number of Participants Who Successfully Donated Blood

Attended a donation appointment within 6 weeks of their message send date and successfully donated, excluding patients who were turned away from or left their appointment without donating.

[Time Frame: Within 6 weeks of the patient's message send date]

2. Number of Participants Who Scheduled a Blood Donation Appointment

Scheduled an appointment within 2 weeks of their message send date.

[Time Frame: Within 2 weeks of the patient's message send date]

3. Number of Participants Who Scheduled a Blood Donation Appointment

Scheduled an appointment within 6 weeks of their message send date.

[Time Frame: Within 6 weeks of the patient's message send date]

Additional exploratory analyses

1. Primary outcome in the full sample

We will run an OLS regression to test whether the primary outcome varies as a function of experimental group in the full sample, without dividing the sample by previous donor status.

2. New donors vs. previous donors

We will run an OLS regression to test whether the primary outcome varies as a function of experimental group, a bivariate indicator for whether or not the patient previously donated blood, and the interaction between these variables.

3. Time to donation

We will run regression models to test whether either intervention message influenced the timing (time elapsed since the message was sent) of donations.

4. Type of donation

We will test whether there are differences in donation type (particularly whole blood and red blood cell donations) as a function of experimental group.

5. Demographics

We will run regression models to test for main effects of several demographic factors on donation behavior, along with interactions between these factors and message group. These demographic factors may include binned age (18–24, 25–34, 35–44, 45–54, 55–64, and 65+), sex, race, ethnicity, line of insurance (as a proxy for socioeconomic status), and Charlson Comorbidity.

References

Gomila, R. (2021). Logistic or linear? Estimating causal effects of experimental treatments on binary outcomes using regression analysis. *Journal of Experimental Psychology: General*, 150(4), 700–709. <https://doi.org/10.1037/xge0000920>

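### The opener robustness check moves its 6-week window to the opening date but leaves the booking exclusion at the send date, so bookings made before opening are credited to the message

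*Combined protocol and SAP*

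**What the plan says.** Three statements in the SAP's Analysis notes matter here.

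- The booking exclusion: "All analyses will exclude patients who scheduled their appointment prior to their message send date". It covers all analyses, names the send date as its reference point and makes no exception.
- The default clock: "Timeframes listed refer to the amount of time elapsed from the send date for a given patient".
- The opener check: "As a robustness check, we will rerun the analyses above on the subset of patients who open the messages". For this rerun the outcome clock is reset, and the plan describes it as "using a time frame of 6 weeks from the date each individual patient opened their message". A parenthesis names the one element being replaced: "rather than 6 weeks from the patient's message send date".

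The same section lists two other exclusions (email not sent, email bounced) and sets the email address as the unit of analysis. The Project status section of the protocol says that all emails had gone out and "No outcome data have been extracted".

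**The concern.** In Analyses 1 and 2 the outcome window and the booking exclusion both start at the send date. Anyone who already had an appointment when the message went out is removed, so the message is not credited with a booking that preceded it.

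The opener check is meant to show whether the result holds among people who read the message, and it counts their 6 weeks from that moment. The exclusion does not move with the window. Bookings made between sending and opening pass through, although in this check they stand in the same relation to opening as the excluded bookings do to sending in Analyses 1 and 2.

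At stake is the meaning and precision of one robustness check that will rest on few events.

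**Working it through.** **Step 1: trace the literal rules.** Take sending as day 0 and opening as day 20, so the opener window runs from day 20 to day 62 (20 + 42).

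| Opener | Booking exclusion (send date) | Opener window | Result |
|---|---|---|---|
| Booked day 5, attended day 30 | Not excluded | Inside | Event, though booked before opening |
| Booked day 5, attended day 10 | Not excluded | Before it starts | Stays in the denominator as a non-event |

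An exclusion placed at opening would remove both patients. Under Analyses 1 and 2 both are ordinary events within 6 weeks of sending, so those analyses have no mismatch.

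**Step 2: inputs for an illustration of size.** The plan states no figure for this check that could be reproduced.

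- From the Power analysis section: 39,317 non-donor and 813 previous-donor addresses, with rates of 0.07% vs 0.16% and 4.76% vs 9.87%.
- Assumed: 1:1 allocation; 20% to 80% of addresses open; the planning rates hold among openers and already include bookings made before opening.
- Assumed: pre-opening bookings that count as events have rate a = f × p1 in each arm, where p1 is the control rate and f = 0.1 to 0.3.
- Attendance before opening is not modelled.

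**Step 3: events available.** Addresses per arm are 39,317/2 = 19,658.5 and 813/2 = 406.5. Control events among openers = addresses per arm × open rate × p1:

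- Non-donors: 19,658.5 × 0.2 × 0.0007 = 2.8, up to 19,658.5 × 0.8 × 0.0007 = 11.0.
- Donors: 406.5 × 0.2 × 0.0476 = 3.9, up to 406.5 × 0.8 × 0.0476 = 15.5.

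Multiplying by f, the pre-opening bookings are 0.3 to 3.3 events per arm in non-donors and 0.4 to 4.6 in donors.

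**Step 4: equal share in both arms.** After exclusion the rate in each arm is q = (p − a)/(1 − a).

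| | Risk difference, kept | Risk difference, excluded | Standard error, kept ÷ excluded |
|---|---|---|---|
| Non-donors, f = 0.1 | 0.0900 points | 0.0900 points | 1.032 |
| Non-donors, f = 0.3 | 0.0900 points | 0.0900 points | 1.106 |
| Donors, f = 0.1 | 5.11 points | 5.13 points | 1.027 |
| Donors, f = 0.3 | 5.11 points | 5.18 points | 1.092 |

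The open rate cancels from the last column. Keeping these bookings leaves the estimate practically where it was and widens the standard error by 3% to 11% (non-donors) and 3% to 9% (donors).

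**Step 5: unequal shares, as a stress test.** Let f be 0.1 in one arm and 0.3 in the other, still as fractions of p1.

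- Non-donors: the risk difference shifts by 0.014 points, 16% of 0.09. Its standard error is 0.0764 points at 20% open and 0.0382 at 80%, so the shift is 0.2 to 0.4 standard errors.
- Donors: the shift is 0.85 or 0.95 points depending on direction, 17% to 19% of 5.11. The standard error is 4.06 or 2.03 points, so the shift is 0.2 to 0.5 standard errors.

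**The case against.** The strongest reply is that moving the time frame to opening carries the booking cut-off with it. That may be what the authors intend, but the text does not say so. The sentence replaces only the 6-week window, and the exclusion is a separate rule with its own reference date and no exception.

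The second reply is that this hardly matters, and much of it stands. With equal shares the estimate does not move. The only visible shift needs a threefold imbalance between arms that nothing in the documents suggests. The shares and open rates are assumptions, and the planning rates come from everyone sent a portal message in the earlier study, not from people who opened an email.

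A reader might also infer three stronger points that the documents do not support.

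- That the plan is silent on openers who attended before opening. It is not: they meet none of the listed exclusions, so the literal rule keeps them as non-events. The rule is questionable, not missing.
- That this check could again change how the donor-status interaction is read, since in the earlier study "when the analysis was limited to patients who opened their messages, this interaction effect disappeared". That result concerned the interaction. The opener check here reruns Analyses 1 and 2, and no opener version of the interaction is planned. The Scientific background also cites uneven numbers of previous donors among the reasons that "call into question the robustness of the interaction effect".
- That the main results are compromised. Analyses 1 and 2 use the send date for both rules.

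That openers are a group selected after randomisation is a separate issue and not part of this point.

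**Conclusion.** The mismatch is plain in the text and confined to one robustness check. Followed as written, the check counts attendances booked before the message was opened and keeps earlier attenders as non-events.

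The consequence is small or unknown. Provided the message cannot influence anyone before it is opened, pre-opening bookings should be equally frequent in both arms unless opening or its delay differs by arm. Without such a difference the cost is precision: a standard error about 3% to 11% wider for assumed shares of 10% to 30% of control events. With one, there is bias; the assumed 10% versus 30% contrast gives 0.2 to 0.5 standard errors, which is modest. Confidence is high for the wording and low for the size, because the documents give no open rates or opening delays. This is a cheap improvement, not a defect in the trial's main analyses.

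**What to change.** For the opener check only, add to the Analysis notes that patients are excluded if their appointment was scheduled, or if they attended, before the date they opened their message. Three details belong with it:

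- The rule concerns the appointment that would be counted. A booking cancelled before opening and remade afterwards should not remove the patient.
- Bookings made on the opening date stay in, matching the existing exclusion, which removes only bookings before its reference date.
- Each patient's own opening date is applied before results are collapsed to the email address. The sample has 40,486 − 40,130 = 356 more patients than addresses, so some addresses may have more than one opening date.

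Also show the openers with the send-date window and the send-date exclusion, so that readers can see whether the choice matters.

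The cost is a short addition to the SAP and one extra run, both possible before outcome data are extracted. A few events are lost (under the assumptions above, 0.3 to 3.3 per arm in non-donors and 0.4 to 4.6 in donors), and the new exclusion depends on a post-randomisation date, which is why the send-date comparison should sit beside it.

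### As written, the 2-week scheduling check keeps only patients who scheduled, so it compares show-up among schedulers and cannot test the message effect on attendance

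*Combined protocol and SAP*

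**What the plan says.** The sentence at issue stands under Analysis notes in the SAP: "We will run an additional robustness check including only patients who scheduled an appointment within the 2 weeks following their message send date". It gives no separate outcome and no denominator.

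Four other places bear on how to read it:

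- **Questions 1 and 2** ask, within each previous-donor stratum, "do more patients attend donation appointments if they are sent the blood-type message compared with those sent the no-blood-type message". The denominator is everyone sent a message.
- **Other prespecified outcomes** lists, as item 2, "Scheduled an appointment within 2 weeks of their message send date" and, as item 3, "Scheduled an appointment within 6 weeks of their message send date". The stated purpose of that section is "to evaluate the impact of the intervention on the other prespecified outcome measures listed in the pre-registration". The plan therefore treats scheduling as something the message may change.
- **Analysis 2** repeats Analysis 1 "including only patients who are previous donors". The same phrase there defines a true subset, fixed before randomisation.
- **Other prespecified outcomes, item 1** (successful donation) uses "excluding patients who were turned away from or left their appointment without donating" inside an outcome definition. There, patients who do not qualify presumably stay in the analysis as non-events.

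Analysis notes also removes anyone who scheduled before the send date, so all remaining scheduling follows the message.

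**The concern.** Attendance is the product of two steps: scheduling an appointment, and showing up for it. An emailed invitation would be expected to act mainly on the first. Restricting the analysis to people who scheduled removes that step and leaves only the second. It also breaks the randomised comparison, because the people whom one message prompts to schedule need not resemble those prompted by the other.

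As a robustness check, such a result cannot be interpreted. A null would not show that the primary effect is fragile, and agreement would not show that it is sound. The risk of misreading is real: the Scientific background section reports that in the previous study an analysis limited to message openers, together with uneven numbers of previous donors across groups, led the team to doubt an interaction. A null among a few dozen schedulers could be read in the same way.

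**Working it through.** **Inputs from the Power analysis section.** Non-donors: 39,317 addresses, 0.07% vs 0.16%. Donors: 813 addresses, 4.76% vs 9.87%. Two-sided alpha 0.05, stated power 80% in each stratum.

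**Assumptions, because the documents do not give them.** A 1:1 split (19,658.5 and 406.5 addresses per arm); show-up *q* among schedulers; share *f* of attendances whose appointment was scheduled within 2 weeks.

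**1. The plan's own figure.** The pooled two-proportion formula gives 80.0% for donors, as stated. For non-donors the printed rates give 74.9%. Rounding covers the gap: with 0.065% for the control rate and 0.155–0.165% for the other arm, power is 76.8–83.3%. The 76% in step 4 comes from simulating the OLS t-test at the printed rates. It is not a separate criticism of the plan.

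**2. What each analysis estimates.** With attendance rate *p*, the 2-week scheduling rate is *p·f/q*.

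- All addresses kept, outcome redefined: *f*·(*p₁* − *p₀*). At *f* = 1 this is 0.16 − 0.07 = 0.09 points (non-donors) or 9.87 − 4.76 = 5.11 points (donors).
- Schedulers only: *q₁* − *q₀*. With equal show-up this is 0, although attendance has roughly doubled.

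**3. Size of the restricted set.** Schedulers per arm = *n·p·f/q*. For non-donors at *f* = 1 and *q* = 0.8: 19,658.5 × 0.0007/0.8 = 17.2 and 19,658.5 × 0.0016/0.8 = 39.3, about 57 in all. At *q* = 0.6: 22.9 + 52.4, about 75. The same formula gives the other counts below. They are before the exclusions for unsent and bounced emails, so they are upper limits under each assumption.

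**4. Rejection rates with equal show-up (60–80%).** Simulation, 200,000 trials per scenario: schedulers binomial per arm, attenders binomial given schedulers, two-sided OLS t-test at 0.05.

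| Stratum | *f* | Addresses used, schedulers only | Rejects, schedulers only | Rejects, all addresses kept |
|---|---|---|---|---|
| Non-donors | 100% | 57–75 | 5% | 76% |
| Non-donors | 75% | 42–57 | 4–5% | 64% |
| Non-donors | 50% | 28–38 | 4–5% | 48% |
| Donors | 100% | 74–99 | 5% | 81% |
| Donors | 75% | 56–74 | 5% | 68% |
| Donors | 50% | 37–50 | 5% | 50% |

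The mean restricted difference is within 0.001 of 0 throughout.

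**5. Unequal show-up, with the same true benefit on attendance.**

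- 75% (no-blood-type) vs 60% (blood-type): the restricted estimate is negative in 80–88% of non-donor trials and 84–92% of donor trials. It is significantly negative in about 10–20% and 14–26%.
- 60% vs 75%: the estimate is positive in 79–88% and 84–92%.

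**6. How a reversal could arise.** Let *f* = 1, let those who would schedule anyway show up 80% of the time, and let the extra schedulers show up 50% of the time.

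- Non-donors: 17.2 schedulers in the no-blood-type arm; 17.2 + 19,658.5 × 0.0009/0.5 = 52.6 in the blood-type arm. Show-up in the latter is 31.5/52.6 = 60%, against 80%.
- Donors: 24.2 and 24.2 + 406.5 × 0.0511/0.5 = 65.7. Show-up is 40.1/65.7 = 61%, against 80%.

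The check would point against a message that more than doubled attendance.

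**The case against.** The best defence is that the authors meant something else: count only attendances whose appointment was scheduled within 2 weeks, and score everyone else 0. There is textual support. The successful-donation definition excludes patients when it means that they do not count as events, and the primary outcome definition likewise speaks of including patients when it means who counts. The sentence just before this one also says explicitly that the analyses will be rerun on a subset (message openers), whereas this sentence does not use those words. On that reading the check is sound.

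This does not settle the matter. The phrasing matches Analysis 2, where it is a true subset. The sentence follows directly on another subset check and is introduced as an additional one. Nowhere does the plan say that non-schedulers stay in as non-events. Literal restriction is the natural reading, and a programmer following the text would apply it.

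Other points stand in part. This is one supplementary check with no decision rule attached, and scheduling at 2 and 6 weeks is analysed by arm, so a reader would see a scheduling effect beside it. The 75% vs 60% show-up contrast has no basis in the documents, and a reversed sign is far more common than a significant reversal; both rates are given above for that reason.

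**Conclusion.** The concern holds for the sentence as written. The check conditions on a post-randomisation outcome, estimates show-up among schedulers, and cannot say whether the effect on attendance is robust. At the plan's target effects and equal show-up, it rejects at about the nominal 5%, against 48–76% (non-donors) or 50–81% (donors) when all addresses are kept; unequal show-up can push it in either direction.

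The figures depend on the assumed 1:1 split, show-up rates and 2-week share. The conclusion about what is being estimated does not. The damage is confined to this check: Analyses 1 and 2 are unaffected. If a change of outcome was intended, the correction simply records it.

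**What to change.** Replace the sentence with a definition of the outcome on the full primary analysis set. Each email address scores 1 if any associated patient attended, within 6 weeks of the send date, an appointment scheduled within 2 weeks of the send date, and 0 otherwise; Analyses 1 and 2 are then rerun on that outcome. If show-up among schedulers is also of interest, report it by arm and label it a descriptive, non-randomised comparison.

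The cost is one SAP sentence, using scheduling and attendance data already planned. The Project status section says "No outcome data have been extracted"; if that is still true, the change can be made without knowledge of results, and otherwise it should be dated and reported as a clarification. The redefined check has less power than the primary analysis when some attendances were scheduled after 2 weeks: for non-donors 64% or 48% instead of 76%, at a 75% or 50% share. A non-significant result on its own should therefore not be taken as evidence against the primary finding.

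### The full-sample model leaves out the stratification factor, so its reported standard error is about 1–2% wider than the stratified design warrants (minor, free to correct)

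*Combined protocol and SAP*

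**What the plan says.** The Methods section states: "Randomization was stratified by previous donor status of all patients at an email address". The Objectives ask whether the blood-type message works better "for patients with needed blood types overall, and separately for previous donors and non-donors", so an overall comparison is one of the trial's stated aims.

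Analyses 1 and 2 are each run inside one stratum. The overall comparison appears only under Additional exploratory analyses, item 1, as an OLS test of whether "the primary outcome varies as a function of experimental group in the full sample, without dividing the sample by previous donor status", with no covariate named. Item 2 of the same list does name covariates: group, "a bivariate indicator for whether or not the patient previously donated blood, and the interaction between these variables". Since the plan lists donor status when it means to use it, the natural reading of item 1 is a model with message group alone.

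The Analysis notes fix the unit ("Analyses will be conducted on the email-address level"). They also take donor status from the pre-randomization data pull for assigning patients to Analysis 1 or 2, reasoning: "Because the data on previous donors from this pull was used to stratify randomization".

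**The concern.** Stratified randomization balances donor status between the arms, so differences between donors and non-donors contribute almost nothing to the sampling variation of the arm difference. A regression on message group alone does not use this. It counts the donor/non-donor gap as residual noise, and its standard error describes an unstratified design. The interval is then a little too wide and the p-value a little too large.

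No other planned analysis supplies the stratum-adjusted overall effect. Exploratory analysis 2 contains the stratum, but with an interaction. Under 0/1 coding its message coefficient is the effect in one stratum, and the plan does not say that an overall effect will be derived from it.

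What is at stake is the accuracy of the reported uncertainty for the overall comparison. The point estimate is essentially the same either way.

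**Working it through.** **Inputs.** From the Power analysis section: 39,317 non-donor and 813 donor addresses, N = 40,130; planning rates 0.07% to 0.16% (non-donors) and 4.76% to 9.87% (donors); two-sided alpha .05. The address is the unit of analysis. Donor share w = 813/40,130 = 0.02026. The allocation ratio and the number of exclusions are not given; I assume 1:1 within strata and no exclusions.

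**The plan's own figures.** The plan states no standard error or power for the full-sample model. Its donor-stratum power does reproduce under 1:1: 813 addresses at 4.76% against 9.87% give 80.0%, which supports that assumption. The non-donor figure gives 74.9% at the printed rates and 80.2% if the control rate is 0.065%, which prints as 0.07%. That is consistent with rounding and does not bear on this point.

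**Formulas.**
- Group-only SE = sqrt(4/N × mean over arms of p(1−p)), where p is the arm's overall rate.
- Design SE = sqrt(4/N × mean within-stratum variance). The within-stratum variance in an arm is p(1−p) − w(1−w)(p_donor − p_non-donor)².
- The additive stratum model reports the design variance plus a small misfit term when the effect differs between strata.

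**Control rates in both arms.**
- p = 0.97974 × 0.0007 + 0.02026 × 0.0476 = 0.00165
- p(1−p) = 0.0016474
- Between-stratum part = 0.02026 × 0.97974 × 0.0469² = 0.0000437, or 2.7% of the total
- Within-stratum variance = 0.0016038
- Group-only SE = sqrt(4 × 0.0016474/40,130) = 0.0405 percentage points
- Design SE = sqrt(4 × 0.0016038/40,130) = 0.0400 percentage points
- Ratio 0.04052/0.03998 = 1.0135

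**Each arm at its stated rate.**
- p = 0.00165 and 0.00357; mean p(1−p) = 0.0026009; within-stratum variance = 0.0024855
- Group-only SE = 0.0509, design SE = 0.0498, additive stratum model 0.0499 percentage points
- The group-only SE is 2.3% wider than the design SE (0.05092/0.04977) and 2.0% wider than the additive model's (0.05092/0.04990).

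**Consequences.** Null rejection at the control rates is 2 × (1 − Φ(1.96 × 1.0135)) = 4.7% instead of 5%. Coverage of the group-only 95% interval is 95.3% at the control rates and 95.5% with each arm at its stated rate. Power with both planning alternatives true is 96.8% without the stratum term and 97.0% with it.

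**Simulation check (400,000 replicates).**

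| Scenario | SD of estimate, either model | Mean SE, group only | Mean SE, with stratum | Result, group only | Result, with stratum |
|---|---|---|---|---|---|
| Control rates | 0.0400 | 0.0405 | 0.0399 | rejection 4.7% | rejection 5.0% |
| Stated rates | 0.0498 | 0.0509 | 0.0498 | coverage 95.5% | coverage 95.0% |

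SDs and SEs are in percentage points. The SD of the estimate does not change, so the stratum term corrects the reported error and does not make the estimate more precise. In a separate simulation of 1,500 trials per scenario, robust standard errors gave the same ratio as classical ones (1.014 and 1.020), so switching to robust errors would not remove the excess.

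**Sensitivity of the SE ratio, group-only to additive model.**
- Effect in non-donors only: 1.010. Effect in donors only: 1.025.
- Both arms at 0.16% and 9.87%: 1.027.
- Equal proportional exclusions in both strata leave it unchanged. Removing 30% of one stratum only gives 1.012 to 1.015 at the control rates.
- Control rates scaled to three-quarters, half and a quarter: 1.010, 1.007 and 1.003.

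**The case against.** The strongest reply is that nothing here is invalid. A group-only comparison after stratified randomization is a legitimate analysis and errs on the safe side. The estimate is no more precise with the stratum term, and the practical effect is tiny. At the control rates about 66 events are expected (39,317 × 0.0007 + 813 × 0.0476). The between-arm difference needed for p < .05 is 15.9 events without the stratum term and 15.7 with it. Power moves by 0.3 points with both alternatives true and by under 2 points in every scenario examined. The analysis is exploratory, while the two primary questions are answered within strata. A reader could also weight the two stratum estimates by stratum size to obtain a stratified overall effect. Finally, the control rates come from a study that used patient portal messages, whereas this one used email. If response is lower, the excess shrinks.

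All of this stands as to size, and it keeps the point minor. It does not remove it. The plan does not say that a weighted overall effect will be reported, the direction of the discrepancy does not depend on the borrowed rates, and the correction has no drawback.

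**Conclusion.** The concern holds as a minor improvement. The full-sample model omits the factor used to stratify randomization, and its reported standard error is about 1–2% too wide at the plan's own rates. Across the other scenarios examined the excess over the additive model runs from 0.3% (control rates cut to a quarter) to 2.7% (both arms at the higher planning rates). The result is slightly conservative: no bias, no inflated type I error, and no effect on Analyses 1 and 2. The figures rest on 1:1 allocation within strata and on exclusions that do not change the donor share much; the documents state neither. The direction follows from the design and the difference in rates between the strata.

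**What to change.** In exploratory analysis 1, add the previous-donor indicator from the pre-randomization data pull as a main effect, without an interaction, and report the message coefficient as the overall effect. Because unsent and bounced emails are removed after randomization, the term would also adjust for any imbalance in donor status left in the analysed set.

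The cost is one covariate, which the plan already uses to define Analyses 1 and 2 and includes in exploratory analysis 2, and a one-line change to the SAP. The Project status section says that no outcome data have been extracted, so at that stage the change can still be prespecified.
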